255 regimen with weekly increments of 0.6 mg until the maintenance dose of 1.8 mg is reached.
256 Liraglutide will be administered once daily by s.c. injections, either in the abdomen, thigh or
257 upper arm. Injections can be done at any time of the day and irrespective of meals. It is
258 recommended that the time of injection is consistent throughout the trial. Subjects will be
259 instructed to perform an air shot before the first use of a new prefilled pen.
260

261 **GROUP 2. Glargine Group**

262

263 **V.e. Treatment recommendations at discharge:**

264

265 **▪ Patients receiving no Therapy prior to admission:**

- 266 • Discharge on glargine once daily at 50% of total hospital dose
 - 267 • Add metformin if A1C \geq 8% and no contraindications.
- 268

269 **▪ Patients receiving OAD prior to admission:**

270

271

272

- If no contraindication, restart pre-admission OADs according to standard of care and investigator’s medical discretion (metformin, sulfonylureas, repaglinide, nateglinide, pioglitazone) in combination to glargine at 50% of hospital dose.
- The total daily dose of insulin secretagogues (sulfonylureas, nateglinides and repaglinide) will be reduced to 50% of pre-admission dose to avoid risk of hypoglycemia.
- DPP4-inhibitors will not be used in combination with liraglutide during the study period

Algorithm for outpatient glargine insulin dose adjustment:

Insulin Glargine	
If mean FBG > 180 mg/dL for the last 2 consecutive days and no episodes of hypoglycemia (BG <70 mg/dL)	Increase daily dose by 4 IU
If mean FBG > 140 mg/dL for the last 2 consecutive days and no episodes of hypoglycemia (BG <70 mg/dL)	Increase daily dose by 2 IU
If mean FBG between 100 to 140 mg/dL for the last 2 consecutive days and no episodes of hypoglycemia (BG <70 mg/dL)	No Change
If any FBG between 70 – 99 mg/dl	Decrease by 4 IU or 10% of total daily dose
If any FBG or RBG < 70 mg/dl	Decrease by 8 IU or 20% of total daily dose
If any FBG or RBG < 40 mg/dl	Decrease total daily dose by 30%

In hospital Diabetes Education. Prior to discharge, participants will be trained on:

1. Diabetes education if not received within 1 year of admission.
2. ADA targets for fasting and premeal BG between 70 to 130 mg/dL.
3. Use of glucose meters for home glucose self-monitoring (meters may vary at different institutions).
4. Keeping BG records, and will receive a log-book to record glucose tests results.
5. Hypoglycemia recognition and management (see VI.B.)

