6. Insulin administration (if needed).

Follow-up Care:

- If baseline visit was not fully completed at the time of discharge, patients will be scheduled to return for a short in-person visit to complete (body measurements) study procedures within 7 days of discharge. Research team will call to verify correct administration of study medication and availability of medications and glycemic control monitoring supplies.

- 300 • After discharge, a member of the diabetes research team will contact patients via
301 telephone call every 2 weeks for a total of 26 weeks.
- 302 • Patients will be asked to attend the next outpatient clinic visit at 4 weeks of hospital
303 discharge. During this visit, patients will receive 8 weeks drug supply of liraglutide and
304 will be asked to return to clinic at 12 weeks for the next outpatient visit. During this visit,
305 patients will receive 12 weeks (3 months) drug supply of liraglutide and will be asked to
306 return to a fourth and final visit at 26 weeks of hospital discharge.
- 307 • Recommendations on insulin adjustment will be provided to patients at each telephone
308 and clinic visits by a licensed physician (fellow or study physician) (see section Vf).

309 **During follow up we will collect the following information:**

- 310 1. Glycemic control:
- 311 a. Mean daily fasting and premeal blood glucose levels.
- 312 b. HbA1c at 3 and 6 months of discharge
- 313 c. Number of hypoglycemic events
- 314 - **Symptomatic hypoglycemia** is defined as an event with typical symptoms (i.e.,
315 sweating, palpitation, and feeling of hunger) with or without confirmation by
316 plasma glucose <70 mg/dl (3.9 mmol/L).
- 317 - **Severe hypoglycemia** is defined as episodes necessitating assistance and
318 associated with measured plasma glucose < 40 mg/dl (2.2 mmol/L) or with
319 prompt recovery after administration of carbohydrates, glucagon, or other
320 resuscitative actions. These episodes may be associated with sufficient
321 neuroglycopenia to induce seizure or coma. Blood glucose measurements may
322 not be available during such an event, but neurological recovery attributable to
323 the restoration of BG to normal is considered sufficient evidence that the event
324 was induced by low plasma glucose.
- 325
- 326 2. Diabetes treatment:
- 327 a. Number of patients receiving insulin therapy, dosage and compliance.
- 328 b. Use of liraglutide and other oral agents, dosage and compliance.

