Gastrointestinal side effects including nausea and vomiting are more common in patients treated with liraglutide compared to placebo. The frequency of nausea and vomiting is reported in up to 14% of patients receiving higher doses of liraglutide 1.8 mg in combination to metformin and sulfonylurea therapy compared to 3.5% in patients receiving placebo plus OADs (Victoza package insert). The number of adverse events will be collected at each telephone contact or clinic visit. There have been few reported events of acute pancreatitis. Subjects should be informed of the characteristic symptoms of acute pancreatitis: persistent, severe abdominal pain. If pancreatitis is suspected, liraglutide and other potentially suspect medicinal products should be discontinued. If the investigator suspects acute pancreatitis, all suspected drugs should be discontinued until confirmatory test have been conducted and appropriate treatment should be initiated. Subjects diagnosed with acute pancreatitis (as a minimum 2 of 3: characteristic abdominal pain, amylase and/or lipase >3xUNR or characteristic findings on CT scan/ MRI should be withdrawn from the study.

Protection against Risks:

We will follow safeguards to minimize the risk to our subjects: a) we will carefully monitor response to medical treatment every 2 weeks by telephone contact and every 3 months during clinic visits, b) women of reproductive age who are sexually active will undergo a urine pregnancy tests prior to participation in the study, c) female subjects whom are pregnant, breast-feeding, or not willing to use appropriate contraception at time of enrollment will not be included in the study, d) patients with significant comorbidities such as chronic kidney disease

420 greater than stage III, liver cirrhosis, gastroparesis, and pancreatic disorders will be excluded
421 from the study.

422
423 Hypoglycemia: Patients will receive diabetes education prior to discharge and will be instructed
424 on hypoglycemia sign/symptoms and treatment. Patients will be asked to call the diabetes center
425 and/or PCP in the event of hypoglycemia. If a patient develops hypoglycemia, the dose of OAD
426 will be reduced or discontinued and the daily dose of basal insulin will be reduced by 10% to
427 30% (see treatment algorithm).

428 Gastrointestinal side effects including nausea and vomiting may be expected, more commonly in

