Collect 7-point profile			x				x							x
Chemistry (BMP or CMP)							x							
Safety														
Adv events	x	x	x	x	x	x	x	x	x	x	x	x	x	x
Hypoglyc.	x	x	x	x	x	x	x	x	x	x	x	x	x	x
Trial material														
Drug dispense	x		x				x							
Drug account	x		x				x							x
Remind 7-point profile prior next visit		x				x							x	

549

- 550 ¹ TELEPHONE CALLS AND OUTPATIEN VISITS CAN BE COMPLETED ± 7 DAYS.
- 551 ² TO BE COMPLETED WITHIN 7 DAYS AFTER D/C (IF NOT COMPLETED AT TIME OF DISCHARGE)
- 552 ³ OBTAINED FROM MEDICAL RECORDS (HBA1C \leq 3MONTHS)
- 553

554 **STUDY DRUGS AND MATERIALS:**

555 Clinical trial materials will be labeled and should be handled and stored according to the
556 respective hospital's regulatory requirements. After discharge, patients will be re-started on their
557 pre-admission OADs (except for DPP4-inhibitors and selected drugs in the presence of
558 contraindication, i.e., metformin and renal failure). Liraglutide or glargine will be provided
559 during the study.

560

561 **Study medication(s) / devices(s)**

562 Liraglutide 6.0 mg/mL solution for s.c. injection, provided in 3 mL prefilled pen.

563

564 **Storage and Drug Accountability of Study Medication(s)**

565 Liraglutide will be stored and dispensed by the research pharmacy at each institution. The
566 liraglutide prefilled pen and glargine will be stored in a refrigerator at a temperature between
567 +2°C and +8°C (+36°F and +46°F).

568 Once dispensed and in use (after first opening), the liraglutide prefilled pen can be stored for one
569 month at room temperature (+15°C to +30°C)/(59°F to 86°F) or in a refrigerator (+2°C to
570 +8°C)/(+36°F to +46°F). The liraglutide prefilled pen must be protected from all sources of light
571 and the pen cap should be kept on when the pen is not in use.

572

573

574 **Drug accountability:** The trial product will be dispensed to each subject as required according
575 to treatment group. The research/clinical staff will perform drug accountability by asking
576 patients to return all unused, partly used and unused cartridges and vials of liraglutide and
577 glargine insulin at each visit.

578

579 **Randomization and Blinding**

580 This is an open label randomized controlled trial. Patients will be randomized consecutively
581 using a computer generated randomization table provided by [name] at the Emory
582 School of Public Health. Patient will be randomized (block randomization) based on glucose

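### The liraglutide quantity dispensed at week 12 is stated as 12 weeks (3 months), but the next and final visit is 14 weeks later and no dispensing is scheduled in between

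*Combined protocol and SAP*

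**What the plan says.** Follow-up Care in the combined protocol and SAP sets out the dispensing steps after discharge. At week 4: "During this visit, patients will receive 8 weeks drug supply of liraglutide and" return at week 12. At week 12: "patients will receive 12 weeks (3 months) drug supply of liraglutide and will be asked to" "return to a fourth and final visit at 26 weeks of hospital discharge".

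The Flow Chart marks drug dispensing at weeks 0, 4 and 12. Every scheduled contact from week 14 to week 24 is a telephone call. Footnote 1 allows each call or visit to take place up to 7 days either side of its date.

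Liraglutide Titration gives a maintenance dose of 1.8 mg once daily, and patients are "instructed to perform an air shot before the first use of a new prefilled pen". The study medication section describes the product: "Liraglutide 6.0 mg/mL solution for s.c. injection, provided in 3 mL prefilled pen". The quantity given at discharge is not stated.

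Drug accountability says that product is dispensed to each subject according to need, and asks patients to return unused product at each visit. It does not say whether returned product is given back.

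**The concern.** The two supply sentences stand next to each other. The first quantity (8 weeks) equals its interval exactly. The second (12 weeks, glossed as 3 months) is shorter than its 14-week interval, and its two expressions do not equal each other. A dispensing quantity is an instruction that a research pharmacy may follow literally, so a mismatch here matters more than a rounded visit label.

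The timing makes it worth correcting. Any days without drug would come at the end of follow-up, directly before the visit that provides the primary endpoint, HbA1c at 26 weeks. Fasting glucose is due at the same visit, and the 7-point profile is to be done within the week before it.

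**Working it through.** **Inputs**
- Last scheduled dispensing: week 12 (Follow-up Care; Flow Chart).
- Final visit: week 26 (same places).
- Stated supply: 12 weeks, or 3 months (Follow-up Care).
- Dose: 1.8 mg daily (Liraglutide Titration).
- Pen: 6.0 mg/mL × 3 mL = 18 mg (study medication section), so 18 / 1.8 = 10 doses.
- Visit window: ±7 days (Flow Chart, footnote 1).

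**Check of the earlier step.** Week 4 to week 12 is 12 − 4 = 8 weeks and the stated supply is 8 weeks. It matches.

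**The step in question.** Week 12 to week 26 is 26 − 12 = 14 weeks, or 14 × 7 = 98 days. Shortfall = max(0, 98 − days supplied):

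| Reading of the quantity | Days covered | Shortfall |
|---|---|---|
| 12 weeks, day count | 84 | 14 |
| 3 months, day count | 91 | 7 |
| 12 weeks in whole pens: 84/10 = 8.4, so 9 pens | 90 | 8 |
| 3 months in whole pens: 91/10 = 9.1, so 10 pens | 100 | 0 |

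Three calendar months can be 89 to 92 days, so the 7-day figure is really 6 to 9. Since pens are whole units, 8 days is the largest nominal gap likely in practice at 1.8 mg, before carry-over and air-shot loss.

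**Where the gap would fall.** From day 84, an 84-day supply ends at about day 168 and a 90-dose supply at about day 174. The week for the last 7-point profile is about days 175 to 182. On either reading, without carry-over or resupply, that week follows run-out.

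**Carry-over from week 4.** An 8-week supply in whole pens is 56/10 = 5.6, so 6 pens, or 60 doses, leaving 4. If these are kept, 90 + 4 = 94 doses, and the 9-pen shortfall is 4 days.

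**Carry-over from discharge.** Assume 3 pens at discharge (the plan gives no number) and weekly dose steps.
- Need, weeks 0 to 4: 7 × 0.6 + 7 × 1.2 + 14 × 1.8 = 4.2 + 8.4 + 25.2 = 37.8 mg.
- Need, weeks 4 to 26: 154 × 1.8 = 277.2 mg.
- Total need: 37.8 + 277.2 = 315 mg.
- Supply: 3 + 6 + 9 = 18 pens × 18 mg = 324 mg.

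There is then no shortfall. The remaining 9 mg is 0.5 mg per pen for air shots, whose volume the plan does not give. With a final visit 7 days late, need is 315 + 7 × 1.8 = 327.6 mg, which is 3.6 mg, or 2 doses, over supply.

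**Pens that cover the interval.** 98/10 = 9.8, so 10 pens. The slack is 2 doses, 3.6 mg, or 0.36 mg per pen. With the week-12 visit 7 days early and the week-26 visit 7 days late, the interval is 112 days: 11.2, so 12 pens.

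**The case against.** The best defence is that the wording is loose and practice would cover it. The plan uses three months as a rough label elsewhere: follow-up data include "HbA1c at 3 and 6 months of discharge", and Protection against Risks describes monitoring "every 2 weeks by telephone contact and every 3 months during" clinic visits. If the pharmacy rounds three months up to 10 pens, nothing is missing. If leftovers are kept, even the strict 12-week reading can suffice, as the 324 mg against 315 mg example shows. The plan also states that study drug will be provided during the study and dispensed as needed, and drug compliance is marked at every contact after discharge.

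Much of this stands, and it limits the size of the point. It does not make the stated quantity right. The supply clauses show intent but set no dispensing after week 12. The one stated check of drug availability ("Research team will call to verify correct administration of study" medication, and that supplies are available) sits in the bullet on completing baseline procedures within 7 days of discharge. The carry-over argument needs an unstated discharge quantity, and leftovers that stay with patients who are asked to return them.

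Stronger readings are tempting but unsupported:
- **Up to four weeks off drug.** A literal 84-day supply against a 112-day interval gives 28 days. This needs both visits at opposite window limits and no carry-over, although an early week-12 visit itself leaves part of the week-4 supply unused if that visit was on time.
- **A biased non-inferiority comparison or lost power.** The documents establish neither that patients run out nor what a short interruption would do to HbA1c.
- **A difference between arms.** No glargine quantity is stated, so no mismatch is shown there and no contrast can be drawn.

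**Conclusion.** The stated week-12 quantity is wrong for the interval it must cover: 12 weeks, or about 13 if the three-month gloss is used, against 14. The nominal shortfall at 1.8 mg daily runs from 0 to 14 days depending on the reading, and is at most 8 days once 12 weeks is rounded up to whole pens. These figures assume visits on their nominal dates, no carry-over, no air-shot loss and no unscheduled resupply. Carry-over could bring the gap to zero.

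This is an inconsistency in the text with a possible, unproven consequence just before the primary-endpoint visit. The effect on HbA1c is unknown and probably modest. The mismatch itself is certain; whether any patient would miss doses is not. It is a minor correction, worth making because it is so cheap.

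**What to change.** In Follow-up Care, replace the 12-week (3-month) liraglutide quantity at the week-12 visit with 14 weeks, plus an allowance for the ±7-day visit window. At 1.8 mg daily this means at least 10 pens for 98 days and up to 12 for 112 days.

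The cost is a one-line edit at an existing visit. Relative to 9 pens it is 1 to 3 more per liraglutide patient, so at most 3 × 140 = 420 pens, with some extra unused product to account for at week 26. No dose, visit or analysis changes.

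A resupply check at a late telephone call would be a weaker substitute. If the week-12 visit is 7 days early, an 84-day supply ends on day 77 + 84 = 161. The window for the week-22 call runs from day 147 to day 161, so it could leave no time for a pick-up or shipment.

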429 patients treated with liraglutide. In subjects with suspected acute pancreatitis liraglutide and
430 other potentially suspect medicinal products should be discontinued until confirmatory tests have
431 been conducted and appropriate treatment initiated.

432
433
434

STATISTICAL CONSIDERATIONS:

435 This study is randomized multicenter, open-label controlled trial. The overall hypothesis is that
436 patients with T2D discharged on liraglutide and glargine will experience similar improvement in
437 glycemic control (HbA1c level at 26 weeks post-discharge). In addition, we anticipate that
438 compared to patients treated with insulin glargine, patients on liraglutide will experience lower
439 number of hypoglycemic events and less weight gain during follow-up.

440

441 **Sample Size and Power Calculations:** The primary endpoint in this study is glycemic control
442 measured by HbA1c at 26 weeks after discharge between treatment groups. To show the non-
443 inferiority of liraglutide to basal glargine insulin in terms of glycemic control, we set the
444 equivalence margin as 0.5%, from a view that an HbA1c difference < 0.5% is usually not
445 considered as clinically significant.

446 Based on preliminary discharge data, we assume the standard deviation of 26 week A1c is
447 bounded about 1.5%. We set the margin of equivalence as 0.5% and assume the true difference
448 between mean A1c is 0. A sample size of 124 for each treatment group would achieve 80%
449 power to reject the hypothesis that the mean HbA1c in patients treated with liraglutide is < 0.5%
450 more than that in patients treated with glargine based on a two-sample one-sided t test, with
451 alpha=0.05. Accounting for 10% attrition rate, we would need 140 patients per treatment group.
452 This leads to a final total sample size estimate of 280 patients that receive study medication.

453

454 The secondary outcome of major interest in this study is the difference in hypoglycemia (BG <70
455 mg/dl). Based on our preliminary discharge data, 30-40% of patients treated with basal insulin
456 will have at least one hypoglycemia episode. Assuming a hypoglycemia rate of 20-35% in the
457 insulin group in this study, given the sample size of 140 subjects per treatment group, based on a
458 two sided Fisher's exact test with alpha=0.05, we would have 80% power to detect an odds ratio
459 in hypoglycemia rate of 0.42 in liraglutide group (versus glargine group). In the following table,

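### On the plan's stated inputs, 80% power for the HbA1c comparison needs 112 evaluable patients per group, not 124; 124 gives 83.5%, so the error is conservative and minor.

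*Combined protocol and SAP*

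**What the plan says.** All inputs stand in one place, the Sample Size and Power Calculations paragraph under Statistical Considerations:

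- **Objective and margin.** Non-inferiority of liraglutide to glargine, with an "equivalence margin as 0.5%, from a view that an HbA1c difference < 0.5% is usually not" clinically important.
- **Variability and true effect.** The standard deviation of 26-week HbA1c is "bounded about 1.5%. We set the margin of equivalence as 0.5% and assume the true difference" in means to be 0.
- **Test.** A one-sided two-sample t test at alpha 0.05.
- **Result.** "A sample size of 124 for each treatment group would achieve 80" per cent power.
- **Attrition.** "Accounting for 10% attrition rate, we would need 140 patients per treatment group", giving 280 in total who receive study medication.

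The order of the sentences presents 124 as the evaluable number and 140 as that number enlarged for attrition. The hypoglycemia power table later in the same section also labels 140 per group as the number before 10% attrition.

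**The concern.** Because every input is given, the result can be checked without outside information, and 124 is about a tenth larger than the inputs require. This paragraph is the only justification in the protocol for the 280 patients repeated under Study Groups, Rationale for Study Population and Study Schedule. If its sample size and power do not belong together, the document misstates the power of its primary comparison. A reader who tries to reproduce the figure also cannot tell which input was really used.

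**Working it through.** **Inputs**, all from the Sample Size and Power Calculations paragraph: SD 1.5, margin 0.5, true difference 0, one-sided alpha 0.05, power 80%, equal groups, attrition 10%. I take the hypothesis to be rejected as the usual non-inferiority null, that liraglutide is worse by at least the margin.

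**1. Attempt to reproduce 124, normal approximation.**

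n per group = 2 × (SD/margin)² × (z₀.₉₅ + z₀.₈₀)²
= 2 × (1.5/0.5)² × (1.645 + 0.842)²
= 18 × 6.183 = 111.3, rounded up to **112**.

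**2. Exact power of the t test.** With n per group, df = 2n − 2 and the noncentrality is 0.5 / (1.5 × √(2/n)). Power is the probability that a noncentral t variable exceeds the one-sided 5% critical value.

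| n per group | Noncentrality | Power |
|---|---|---|
| 111 | 2.483 | 79.7% |
| 112 | 2.494 | 80.0% |
| 124 | 2.625 | 83.5% |
| 126 | 2.646 | 84.0% |
| 140 | 2.789 | 87.2% |

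The exact method also gives **112**. The stated 124 is 12 higher (12/112 = 10.7%).

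**3. Standard variants.** None returns 124: one-sided alpha 0.025 gives 143, a two one-sided tests equivalence design gives 155, and a Wilcoxon efficiency adjustment gives 117 to 118.

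**4. Attrition.**

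- One allowance on 112: 112/0.9 = 124.4, rounded up to 125 per group and 250 in total. Against 280 the difference is 30 patients (30/250 = 12%).
- The plan's own step: 124/0.9 = 137.8, so 138. The stated 140 is a reasonable rounding of that, and the discrepancy therefore lies in the 124.
- The plan as it stands: 140 × 0.9 = 126 evaluable, with 84.0% power.

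**5. What could have produced 124.**

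- *An attrition allowance already inside it.* 112/0.9 = 124.4 and 112 × 1.1 = 123.2 both lie close to 124.
- *A slightly larger SD.* At SD 1.575 the exact method needs 124 per group; at 1.58 it needs 125.
- *A slightly nonzero true difference.* At SD 1.5, a true difference of 0.025 in favour of glargine also needs 124, but the paragraph states 0.

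**The case against.** The strongest defence is that nothing harmful follows. A group of 124 does reach 80% power, since it exceeds it, and the planned size leaves the primary test with more power than claimed. That stands, and it is why the point is minor.

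A second defence is that the SD is given only loosely, so 124 may come from an unrounded value. This is possible but does not rescue the text. An SD of 1.575 would normally be written as 1.6; the largest that still rounds to 1.5 (1.549) needs 120. The word used also suggests that 1.5 is close to an upper limit. If another value was used, it should be stated.

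A reader might infer that the 10% attrition was definitely applied twice. The documents do not support so firm a conclusion. They show one attrition step, from 124 to 140, and the figure 112 appears nowhere. The fit is also imperfect: multiplying by 1.1 and rounding up gives 112, 124, 137, while dividing by 0.9 and rounding up gives 112, 125, 139. Neither rule yields both 124 and 140 without further rounding.

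A reader might also infer that the trial is underpowered or that enrolment should be cut. The figures show the opposite of the first, and the surplus is no reason for the second.

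**Conclusion.** The stated pairing of 124 per group with 80% power does not follow from the stated inputs. The correct pairings are 112 with 80.0% and 124 with 83.5%, and the planned 140 less 10% attrition gives 126 evaluable with 84.0%. This rests on taking the SD as 1.5 and the true difference as 0, as written. The error is conservative: about 250 patients in total would meet the plan's own 80% target after one 10% allowance, against 280 planned. Its cause is open, since both an attrition allowance already included in the 124 and an SD of about 1.575 fit, and the documents confirm neither. No analysis or decision depends on it, so the severity is minor.

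**What to change.** Keep 140 per group receiving study medication and restate the paragraph along these lines: 112 evaluable per group give 80% power; 140 per group with 10% attrition leaves 126 evaluable and 84% power. If a different input produced 124, state that input and the formula or software instead, so that the figure can be reproduced. The single step from evaluable patients to 140 stays in either case.

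The cost is the wording of one paragraph, with no change to enrolment. The new wording should keep to patients receiving study medication, as the paragraph now does, because the protocol gives other totals elsewhere for recruitment and analysis and this correction should not settle those by implication.
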